8.3.3 Handling of Replicate Data

A subject having an AE coded to the same PT more than once during the study will be counted only once in the incidence calculations for that AE. Similarly, if a subject has more than one AE in a single body system, the incidence will be counted only once for that body system. If a subject has the same AE more than once, the occurrence that is of greatest severity will be used in the calculation of the incidence of individual AE by severity. Similarly, the AE considered most closely related to study drug will be used in the calculation of incidence of individual AE by relationship in case a subject has the same AE more than once.

For the laboratory, vital signs, ECG, EEG and other safety variables datasets, the measurement noted as the scheduled visit measurement will be used in the analysis. If more than one assessment is present at a scheduled visit, then the nearest assessment for evaluation visit (day) will be used in the summaries of the actual values and changes from baseline. In the event of two assessments being equally close to the scheduled visit (day), the last assessment will be used.

Handling of prior/concomitant medication

If the subject has taken the same concomitant medication (as coded to preferred WHO-drug term) more than once, the subject will be counted only once in the tabulation.

8.3.4 Safety Data Collected After the ED Visit

Post TE data (data collected beyond treatment emergent window) will be summarized separately for non-TEAEs only, otherwise no post TE data will be summarized. If data is within the treatment emergent period, they will be windowed into the visits as above. Data that is not treatment emergent will be flagged in the listings.

8.4 Algorithms for Efficacy Parameters

This section describes the algorithms and missing data handling procedure to derive the totals scores for the efficacy parameters MoCA, NPI, MMSE, CFI, WAIS-IV DSC, SAPS-PD and FAQ.

Montreal Cognitive Assessment (MoCA)

This scale assesses different cognitive domains: attention and concentration, executive functions, memory, language, visuoconstructional skills, conceptual thinking, calculations, and orientation. It is reported to be useful to characterize global cognitive impairment in DB. The MoCA scale is composed of 11 assessments. The following are the assessments and possible points earned for each assessment:

Visuoconstructional skills (0 – 5 points), Naming (0 – 3 points), Memory (No points), Attention: Forward/backward digit span (0 – 2 points), Attention: Vigilance (0 – 1 point), Attention: Serial 7s (0 - 3 points), Language: Sentence repetition (0 – 2 points), Language:

Verbal fluency (0 – 1 points), Abstraction (0 – 2 points), Delayed recall (0 – 5 points), and Orientation (0 – 6 points).

The MoCA Total Score (range 0 to 30) = sum of all points earned. If any assessment is missing, then the Total Score is missing. The lower the total score, the worse the cognitive impairment.

Clinician's Interview Based Impression of Change Plus Caregiver Input (CIBIC-Plus)

This scale is designed to measure various domains that describe subject function: general, mental/cognitive state, behavior, and activities of daily living. The CIBIC-Plus scores will be assigned by clinicians and the possible scores are: 1 (marked improvement), 2 (moderate improvement), 3 (minimal improvement), 4 (no change), 5 (minimal worsening), 6 (moderate worsening) and 7 (marked worsening).

Neuropsychiatric Inventory (NPI)

This scale assesses frequency and severity of 12 neuropsychiatric symptoms commonly described in dementia patients: delusions, hallucinations, agitation/aggression, depression/dysphoria, anxiety, elation/euphoria, apathy/indifference, disinhibition, irritability/lability, motor disturbance, nighttime behaviors and appetite/eating changes. The scale is composed of 12 items, each item score ranges from 0 to 12.

The NPI Total Score (range 0 to 144) = sum of all item scores. If any item score is missing it is set to zero. The higher the total score, the more severe the symptoms.

A subscore covering the domains of delusions, hallucinations, apathy and depression (NPI-4) will also be derived. The subscore (0 to 48) = sum of 4 corresponding item scores. If any one of the 4 item scores is missing then it is set to zero

The caregiver distress (NPI-D) is rated by caregiver based on his or her own stress on a five point scale from 0 - no distress, 1- minimal, 2 - mild, 3 - moderate, 4 - moderately severe, 5 - very severe or extreme.

NPI-10 is the subscore (0-120) of all items except night-time behavior and appetite/eating changes. If any one of the 10 item scores are missing then it is set to zero.

Mini-Mental State Examination (MMSE)

The MMSE is composed of 30 questions grouped into domains, see Table 6. For each of the MMSE domains the correct responses are added. If a domain has missing data then the domain is missing. From the domains compute the six items as show in Table 6. If any domain is missing then the item is missing. The MMSE Total Score (range 0 to 30) = sum of the six items. If any item score is missing then the Total Score is missing. The lower the total score, the worse the impairment.

Table 6 MMSE Domains and Items

Domain	Score Range	Item	Score Range
1. Orientation to Time	0 to 5	1. Orientation to Time	0 to 5
2. Orientation to Place	0 to 5	2. Orientation to Place	0 to 5
3. Registration	0 to 3	3. Registration	0 to 3
4. Attention and Calculation ^a	0 to 5	4. Attention and Calculation	0 to 5
5. Recall	0 to 3	5. Recall	0 to 3
6. Naming	0 to 2	6. Language (Sum of Naming, Repetition, Comprehension, Reading, Writing, and Drawing)	0 to 9
7. Repetition	0 to 1		
8. Comprehension	0 to 3		
9. Reading	0 to 1		
10. Writing	0 to 1		
11. Drawing	0 to 1		
		Total Score	0 to 30

Cognitive Fluctuation Inventory (CFI)

This scale assesses cognitive fluctuation with the same format as the NPI. It evaluates fluctuation in various domains including attention, ability to perform daily functions, orientation, verbal communication and behaviour. It is scored based on frequency and severity with a score range of 0–12. The scale also assesses the degree of caregiver/informant distress engendered by the symptoms. If any one of the domain scores are missing then the score is missing.

Wechsler Adult Intelligence Scale-4th Edition Digit Symbol Coding (WAIS-IV DSC)

The measure of interest in the WAIS-IV is known as the Digit Symbol Coding, which is the number of squares filled in correctly within the time limit of 120 seconds (score range of 0 to 135). This test engages multiple cognitive abilities including attention, psychomotor speed,

complex scanning, visual tracking, and immediate memory. If any part of the test is missing (subject unable or unwilling) then the score is missing.

Scale for Assessment of Positive Symptoms in Parkinson's Disease (SAPS-PD)

There are 5 items for hallucinations (including auditory, voices conversing, somatic/tactile, visual and global hallucinations) and 4 items for delusions (including persecutory, jealousy, reference and global delusions). Each item is scored on a scale of 0 to 5, with 0 being none and 5 representing severe and frequent symptoms. Therefore, the SAPS-PD total score can range from 0 to 45 with higher scores reflecting greater severity of illness. If any one of the item scores are missing, then the total score is missing.

Functional Assessments Questionnaire (FAQ)

On the basis of interviews with the caregivers/informants, subjects will be rated for ability to carry out ten complex activities of daily living: (1) manage finances, (2) complete forms, (3) shop, (4) perform games of skill or hobbies, (5) prepare hot beverages, (6) prepare balanced meal, (7) follow current events, (8) attend to television programs, books, and magazines, (9) remember appointments, and (10) travel out of the neighborhood. Each activity will be rated as 0 (normal, does without difficulty), 1 (has difficulty but does by self), 2 (requires assistance), or 3 (dependent). Scores will be summed across items to provide a total disability score (higher scores = greater impairment; maximum score = 30). If an activity was never or very rarely performed premorbidly, it will be marked as "Not Applicable" and will not be included in the score. A proportional score will be derived for subjects who mark any activity as 'Not Applicable' as follows (achieved score/(30 – 3 times the number of activities marked 'Not Applicable')).

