5 STATISTICAL METHODS

All descriptive statistics for continuous variables will be reported using mean, standard deviation (SD), median, minimum, maximum and number of subjects with non-missing data. Categorical variables will be summarized as number (percentage) of subjects.

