5.1.3 Exploratory Endpoints

- The following clinical efficacy endpoints at 12 weeks of treatment
 - Change from baseline in MoCA total score
 - Change from baseline in WAIS-IV DSC score
 - CIBIC-Plus scale
 - CGIC scale
 - Change from baseline in CFI score
 - Change from baseline in MMSE total score
 - Change from baseline in NPI total score, subscores and caregiver distress score
 - Change from baseline in SAPS-PD total score
 - Change from baseline in FAQ total score
- Change from baseline in CSF cGMP at 9 weeks of treatment
- Percentage change and change from baseline at 9 weeks of treatment in other biomarkers in CSF and/or plasma, including using other diagnostic subgroups classifications based on baseline biomarkers (if appropriate)
- PK of E2027 in subjects with DLB or PDD, using population modelling
- Relationships between E2027 in plasma/CSF and its effects on the following variables using PK/PD modelling, if data permit:
 - Plasma/CSF PD biomarkers (including CSF cGMP),
 - Clinical efficacy (including MoCA, WAIS-IV DSC, CIBIC-Plus, NPI, MMSE, CFI, SAPS-PD, FAQ, and CGIC at 12 weeks of treatment),
 - Safety variables
- Relationships of the plasma and CSF PD biomarkers compared to MoCA, WAIS-IV DSC, CIBIC-Plus, NPI, MMSE, CFI, SAPS-PD, FAQ, and CGIC at 12 weeks of treatment, if data permit
- Relationships amongst plasma biomarkers and CSF biomarkers at baseline and after treatment (if appropriate)
- Subgroup analyses based on genotype classification for CSF cGMP changes from baseline and clinical endpoints

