Biomarker data will be summarized under the PD Analysis Set for each subgroup and overall using descriptive statistics. Continuous variables include CSF cGMP, plasma A β 42, plasma A β 40, CSF A β 42, CSF A β 40, CSF A β 42/40 ratio, plasma p-tau181, plasma p-tau181/A β (1-42), CSF p-tau181, CSF p-tau181/A β (1-42), plasma neurogranin, plasma neurofilament light (NfL), plasma GFAP, CSF neurogranin, CSF neurofilament light, and any other appropriate biomarkers. Categorical variables include A β 42/40 ratio (<0.092, \geq 0.092), CSF A β 42/40 ratio (<0.0571, \geq 0.0571) [Ref 1], ApoE4 (positive, negative), ApoE categories, plasma p-tau181 (<2.2, \geq 2.2 μ g/mL), plasma p-tau181/A β (1-42) ratio (<0.043, \geq 0.043), CSF total tau (<400, \geq 400 μ g/mL), CSF ptau-181 (<52.8, \geq 52.8 μ g/mL), CSF p-tau181/A β (1-42) ratio (<0.083, \geq 0.083), CSF total tau/A β (1-42) ratio (<0.637, \geq 0.637) and other groups of biomarkers as appropriate. If numbers allow, combinations as follows will be calculated:

a) Based on plasma A β 42/40 and apolipoprotein E4 (ApoE4):

- A β 42/40 <0.092 and ApoE4 positive,
- A β 42/40 <0.092 and ApoE4 negative,
- A β 42/40 \geq 0.092 and ApoE4 negative,
- A β 42/40 \geq 0.092 and ApoE4 positive,

b) Based on CSF A β 42/40 and ApoE4

- CSF A β 42/40 <0.0571 and ApoE4 positive,

- CSF A β 42/40 <0.0571 and ApoE4 negative,
- CSF A β 42/40 \geq 0.0571 and ApoE4 negative,
- CSF A β 42/40 \geq 0.0571 and ApoE4 positive.

Clinical efficacy data will be summarized under the FAS for each subgroup and overall using descriptive statistics. Continuous variables include MoCA total score, NPI total score, NPI-4 score, NPI-10 score, NPI-D score, NPI subscores, MMSE total score, CFI score, WAIS-IV DSC, SAPS-PD and FAQ. Categorical variables include CIBIC Plus and subitems, and MMSE total score subgroup (14-19, 20-26).

Where Screening values are collected, these may be summarized also.

Where the date of diagnosis only contains the year of diagnosis, the age of diagnosis will use the year of diagnosis – year of birth.

MEDICAL HISTORY

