Summaries and figures will be produced exploring the relationships between CSF and plasma PD biomarkers and the efficacy endpoints. If data permit, the relationship between CSF and plasma PD biomarkers compared to each efficacy endpoint (MoCA, WAIS-IV DSC, CIBIC-Plus, CGIC, CFI, MMSE, NPI [NPI-12, NPI-10, NPI-4 and NPI-D, and each subscore], SAPS-PD and FAQ) and MDS-UPDRS-III will be explored using correlation analysis. The association between individual CSF/plasma biomarker concentration data and individual efficacy data within each subgroup (DLB without amyloid copathology vs DLB with amyloid copathology; PDD without amyloid copathology vs PDD with amyloid copathology; total (DLB+PDD) without amyloid vs with amyloid; DLB without amyloid vs PDD without amyloid; and DLB with amyloid vs PDD with amyloid) will be examined through scatter plots. The scatter plots including the Pearson correlation coefficient and Spearman correlation coefficient will be produced for each amyloid subgroup for both percentage change from baseline and change from baseline (as appropriate) in CSF and plasma PD biomarkers after 9 weeks of treatment and change from baseline at 12 weeks of treatment for the efficacy endpoints. Correlations against CSF and plasma biomarkers at baseline compared to change from baseline at 12 weeks of treatment for the efficacy endpoints may also be explored, by subgroups.

If appropriate, relationships amongst plasma biomarkers and CSF biomarkers (including cGMP) at baseline and after treatment will be explored using summaries, correlation analysis and scatter plots.

Pharmacogenomic Analyses

The percentage change in CSF cGMP at 9 weeks, change in CSF cGMP at 9 weeks and other CSF and plasma PD biomarkers will be summarized by ApoE4 status, using the PD Analysis Set. Other pharmacogenomic data will be summarized similarly.

Pharmacodynamic/Pharmacokinetic Analyses

The correlation amongst plasma and CSF exposure to E2027 and the various efficacy and biomarker endpoints will be explored graphically. The details will be described in the separately prepared analysis plan.

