5.8 Exploratory Analyses

The exploratory efficacy endpoints, MoCA (and subitems), WAIS-IV DSC, CIBIC-Plus (and subitems), CGIC, CFI, MMSE, NPI (NPI-12, NPI-10, NPI-4 and NPI-D, and each subscore), SAPS-PD and FAQ, will be summarized based on the FAS, by subject subgroup (DLB without amyloid copathology, DLB with amyloid copathology, PDD without amyloid copathology, and PDD with amyloid copathology). No formal statistical analyses will be performed. Figures will be produced by visit, they will present without amyloid DLB, with amyloid DLB, without amyloid PDD, with amyloid PDD, with amyloid and without amyloid copathology (regardless of DLB/PDD).

The exploratory efficacy endpoint, MoCA will be repeated for subgroups as per Section 5.3.4.

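### SAP Section 8.4 scores the FAQ from 0 to 1 for subjects with a Not Applicable activity and from 0 to 30 for everyone else, with no common scale stated

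*SAP*

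**What the plan says.** SAP Section 8.4 opens by saying that its algorithms are there "to derive the totals scores for the efficacy parameters MoCA, NPI, MMSE, CFI, WAIS-IV DSC, SAPS-PD and FAQ". For the FAQ, ten activities are each rated 0 to 3 and summed to "provide a total disability score (higher scores = greater impairment; maximum score = 30"). An activity that the subject never or very rarely performed before the illness is marked NA and left out of the score. Then: "A proportional score will be derived for subjects who mark any activity as" NA, computed as achieved score/(30 − 3 × number of NA activities). No multiplier follows. Protocol Section 9.5.1.2.9 and the FAQ paragraph of the protocol synopsis give the same formula, also without one.

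The FAQ is used in three places:

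- SAP Section 5.1.3 names one FAQ endpoint: "Change from baseline in FAQ total score", at 12 weeks.
- SAP Section 5.2.4 lists it among the continuous baseline variables ("MMSE total score, CFI score, WAIS-IV DSC, SAPS-PD and FAQ"), and Section 5.8 summarizes it by subgroup. Under Section 5, continuous variables "will be reported using mean, standard deviation (SD), median, minimum, maximum and number of subjects with non-missing data".
- SAP Section 5.5.2 includes it, if data permit, among the efficacy endpoints set against the biomarkers: "The scatter plots including the Pearson correlation coefficient and Spearman correlation coefficient will be produced for each amyloid subgroup".

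Section 5.8 also says: "No formal statistical analyses will be performed".

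**The concern.** The numerator and the denominator of the proportional score have the same maximum, so the score cannot exceed 1. A subject with no NA activity is scored up to 30. Neither document rescales the fraction, converts every subject to a proportion, or reports the two scores separately. Because Section 8.4 is where the total scores are derived and there is a single FAQ total score endpoint, the natural reading is that both kinds of score go into one variable.

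On that reading, a subject with the same NA activities at both visits has the change shrunk 30-fold relative to everyone else. If an activity is marked NA at only one visit, the change is a 0–1 value set against a 0–30 value and has no meaning. SAP Section 4 plans 8 enrolled subjects and 6 completers per subgroup, so one such subject is enough to disturb a mean, an SD or a correlation.

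**Working it through.** **Inputs from the documents.** Ten activities, each rated 0 to 3 (SAP 8.4); denominator 30 − 3k, where k is the number of NA activities (SAP 8.4); 6 completers and 8 enrolled per subgroup (SAP 4). The documents give no NA rate and no FAQ data, so every subject-level value below is an assumption for illustration.

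**Stated maximum.** 10 × 3 = 30, which reproduces the plan's figure.

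**Range of the proportional score.** With k NA activities the largest achievable sum is 3 × (10 − k) = 30 − 3k, so the maximum is (30 − 3k)/(30 − 3k) = 1 for any k from 1 to 9. A subject rated 2 on every applicable activity scores 20 if k = 0, but 18/27 = 0.667 if k = 1 and 16/24 = 0.667 if k = 2.

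**One subject's change.** Take one NA activity at both visits, with the sum going from 12 to 18 of a possible 27.

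- As written: 18/27 − 12/27 = 0.667 − 0.444 = 0.222.
- Multiplied by 30: 6.67.
- Raw sum only: 18 − 12 = 6, which is 10% short of 6.67. The general factor is (30 − 3k)/30, so the shortfall is 20% for k = 2 and 30% for k = 3.

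**NA status differing between visits.** Sum 20 with k = 0 at baseline and 18 with k = 1 at Week 12: as written, 18/27 − 20 = −19.33; multiplied by 30, 20 − 20 = 0.

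**Subgroup mean change when every subject truly worsens by 6.67 and one is NA.**

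| Subgroup size | As written | Raw-sum reading |
|---|---|---|
| 6 | (5 × 6.667 + 0.222)/6 = 5.59, 16% too small | (5 × 6.667 + 6)/6 = 6.56, 1.7% too small |
| 8 | (7 × 6.667 + 0.222)/8 = 5.86, 12% too small | (7 × 6.667 + 6)/8 = 6.58, 1.25% too small |

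The median stays at 6.67 as written, because all the other values are equal.

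**With spread in the data (6 subjects, the last one NA).**

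| Quantity | Common 0–30 scale | As written |
|---|---|---|
| Changes 2, 4, 6, 8, 10, 6.67: mean | 6.11 | 5.04 |
| SD | 2.84 | 3.68 |
| Median | 6.33 | 5.0 |
| Minimum | 2 | 0.22 |
| Levels 16, 18, 20, 22, 24, 20: mean | 20 | 16.78 |
| SD | 2.83 | 8.38 |
| Median | 20 | 19 |

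**Correlation.** Take cGMP percentage changes 80, 110, 140, 170, 200, 230 and FAQ changes 6, 4, 2, 0, −2, −4, so the true correlation is −1.00. Dividing one FAQ change by 30, at each position in turn, gives:

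- Pearson: −0.77, −0.91, −0.98, −1.00, −0.98, −0.92
- Spearman: −0.83, −0.94, −1.00, −1.00, −1.00, −0.94

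The loss is largest when the NA subject has the largest change and is nil when that change is zero.

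**Check of the remedy.** 30 × achieved/(30 − 3k) runs from 0 to 30 for every k from 0 to 9 and equals the plain sum at k = 0. The subject rated 2 throughout scores 20 whether k is 0, 1 or 2.

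**The case against.** The strongest counter-argument is textual. Section 8.4 uses two names, a total disability score and a proportional score, and the endpoint is the FAQ total score. The proportional score could be an extra variable, with the raw sum kept as the endpoint. That reading cannot be excluded, and on it the errors in the example means fall below 2%. It does not settle the matter: nothing says which score is the endpoint, and NA subjects would have a maximum of 27, 24 or 21 (one, two or three NA activities) beside others on 30.

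Second, SAP Sections 9 and 11 place the programming rules and table shells in separate documents, which may contain a rescaling. That is possible, but Section 8.4 states the formula itself, and a programmer who follows it produces a value between 0 and 1.

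Third, the size is assumed throughout. With no NA subjects the effect is zero, the correlation example starts from a perfect relationship, and in half of its positions the loss is negligible. This stands; the figures show what one subject can do and are not a forecast.

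Fourth, the consequence is limited. FAQ is one of nine exploratory clinical endpoints, it is only described, and a baseline minimum below 1 beside scores near 20 would probably be noticed. This also stands. Against it, protocol Section 7.3 says that the relation of cGMP to the efficacy endpoints will be explored and that the results will guide the choice of subgroups for Phase 3.

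**Conclusion.** The rule is wrong as written. It gives one endpoint two units, and no passage in either document reconciles them. If the fraction is pooled with the sums, and NA status is the same at both visits, each affected subject's change is 30 times too small. In the illustrative subgroups with a uniform change, one affected subject makes the mean 12% to 16% too small; with spread, the SD rises and a correlation of −1.00 can fall to −0.77 (Pearson) or −0.83 (Spearman). If the raw sum is the intended endpoint, the error is much smaller but the endpoint is still undefined for these subjects. The pooled reading is an inference from Sections 8.4 and 5.1.3, and the number of NA subjects is unknown. The effect is confined to the FAQ summaries, figures and correlations; the primary CSF cGMP analysis is not touched. The correction should be made, but it is not critical to the trial's main conclusion.

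**What to change.** In SAP Section 8.4, define the score for subjects with an NA activity as 30 × achieved score/(30 − 3 × number of NA activities), and state that this value is their FAQ total score in all summaries and correlations. Scoring every subject from 0 to 1 would also be consistent, but it would contradict the stated maximum of 30. Because NA describes what the subject did before the illness, it should not change during the study; add a data check that queries any NA status differing between baseline and Week 12.

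The same formula in protocol Section 9.5.1.2.9 and the synopsis should agree. A clarification in the SAP is enough for the analysis, and the protocol text can be aligned without an amendment solely for this purpose. Confirm that the programming specifications follow the same rule. The cost is one factor, one sentence and one data check, with no new data or tables.

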8.5 Algorithms for Safety Parameters

MDS-UPDRS-III subscores are defined as follows:

Tremor: sum of MDS-UPDRS-III category 3.15 to 3.18 (sum of 10 items from 4 categories: 3.15 Postural Tremor of the Hands, 3.16 Kinetic Tremor of the Hands, 3.17 Rest Tremor Amplitude, 3.18 Constancy of Rest Tremor).

Rigidity: sum of MDS-UPDRS-III category 3.3 (sum of 5 items from 1 category: 3.3 Rigidity).

Bradykinesia: sum of category 3.4 to 3.8 and 3.14 (sum of 11 items from 6 categories: 3.4 Finger Tapping, 3.5 Hand Movements, 3.6 Pronation-Supination Movements of Hands, 3.7 Toe Tapping, 3.8 Leg Agility, 3.14 Global Spontaneity of Movement [Body Bradykinesia]).

Postural instability and gait difficulty (PIGD): sum of category 3.9 to 3.13 (sum of 5 items from 5 categories: 3.9 Arising from Chair, 3.10 Gait, 3.11 Freezing of Gait, 3.12 Postural Stability, 3.13 Posture).

